Phase 2: Biomarker assessments may include further understanding the MOA (ADCC/CDC/ADCP) of daratumumab in combination with lenalidomide and dexamethasone, immunophenotyping, evaluation of complement proteins, soluble CD38, and multiple myeloma cell profiling (including CD38/CD46/CD55/CD59 expression). In addition, exploratory proteomics and SNP analysis may be performed. Biomarker analyses are dependent upon the availability of appropriate biomarker assays and may be deferred or not performed if during or at the end of the study it becomes clear that the analysis will have no scientific value, or if there are not enough samples or not enough responders to allow for adequate biomarker evaluation. In the event the study is terminated early or shows poor clinical efficacy, completion of biomarker assessments is based on justification and intended utility of the data.

PHARMACOGENOMIC (DNA) EVALUATIONS

A pharmacogenomic blood sample will be collected to allow for pharmacogenomic research, as necessary (where local regulations permit). Subject participation in the pharmacogenomic research is optional.

SAFETY EVALUATIONS

Safety variables are the incidence of AEs, physical examination findings, electrocardiogram results, vital sign measurements, ECOG performance status, laboratory test results, and immunogenicity assessments.

Dose-limiting Toxicity:

Dose-limiting toxicities are defined as any of the following events that occur during the first treatment cycle (28 days):

- Nonhematologic toxicity considered to be a serious adverse event (SAE) of grade 3 or higher and related to daratumumab with the exception of:
 - Any nonhematologic reaction of grade 3 or higher that has an onset after the start of infusion on an infusion day, responds to symptomatic therapy, and resolves within 6 hours from onset
- Adverse reactions that prevent the infusion from being resumed regardless of the length of the reaction
- Hematologic toxicity, considered related to daratumumab, defined as
 - Thrombocytopenia (platelet count $< 20,000 \text{ cells/}\mu\text{L}$)
 - Asymptomatic grade 4 neutropenia for more than 3 days
 - Neutropenic fever (defined as grade 3 or 4 neutropenia and temperature > 38.5°C) for more than 3 days
- Inability to receive the Day 1 infusion of Cycle 2 because of any toxicity related to daratumumab

STATISTICAL METHODS

The 2 phases of this study will be analyzed separately. When appropriate, all subjects who are treated with daratumumab may be combined together for comprehensive safety assessment. The latest available measurements before study drug administration will serve as baseline values.

Phase 1 follows a standard 3+3 design. For Phase 2, it is assumed that lenalidomide + dexamethasone would achieve an ORR of 50% in the targeted population. With a two-sided alpha of 0.10 and assuming that the addition of daratumumab improves the ORR to 75%, a sample size of approximately 30 subjects would achieve 89% power to detect such a difference. If the addition of daratumumab can improve the ORR to 80%, this sample size would achieve 97% power to detect such a difference. The proportion of subjects with response to treatment (stringent CR [sCR], CR, very good PR [VGPR], and PR) will be estimated. The quality of response (also including subjects who achieve MR) will be summarized. The proportions will be presented with corresponding exact 2-sided 95% confidence intervals. Duration of response, time to progression, and PFS will be estimated using Kaplan-Meier techniques.

Subject information variables will be estimated by using descriptive statistics. Continuous variables will be summarized by using the number of observations (n), mean, standard deviation, median, minimum, and maximum, where n denotes the number of subjects with available data. Categorical variables will be summarized by using n and percentages, where the calculation of the percentages will be based on the number of subjects in the population (N) and the number of subjects with available data (n). Results will be presented by cohort as well as by all subjects combined.

NOTE: As of Amendment 7, the primary analysis will be achieved. All subjects in the study have either received at least 12 months of study drug or have discontinued. Ongoing subjects may continue treatment with study drug with a limited schedule of assessments. Disease assessments/response evaluations will be performed per local institutional practice. Safety information will be limited to study drug administration, serious adverse events (SAEs, including secondary malignancies), concomitant medications associated with SAEs, and pregnancy testing. No additional PK blood sampling will be performed, samples will be collected only for immunogenicity and the same samples will be used for determination of the associated daratumumab serum concentrations. Follow up will include collection of survival information, best response and new antimyeloma therapies, and secondary malignancies every 6 months for 3 years after the last dose of study drug or termination of the study by the sponsor, whichever occurs first.

NOTE: As of Amendment 8, the final analysis will have been achieved. All subjects in the study have either received at least 24 months of study drug or have discontinued study drug. Ongoing subjects may continue treatment with study drug. Disease assessments/response evaluations will be performed per local institutional practice. Safety information will be limited to collection of data regarding SAEs and SPMs. All subjects will be followed for 3 years after the last dose of lenalidomide, to enable collection of SPMs.

The study will end when daratumumab is approved for use in combination with lenalidomide and dexamethasone and is commercially available. Subjects still receiving treatment will be transitioned from study drug to commercial product once commercial product is available in their region (or when daratumumab can be accessed from another source) and will be withdrawn from this study at that time. In these circumstances, the sponsor and investigator will support transition of the subject to ensure that treatment continues uninterrupted. All subjects will be followed for 3 years after the last dose of lenalidomide, to enable collection of SPMs.

Table 1: Phase 1 Time and Events Schedule

Note: As of Amendment 8, all subjects are to follow the Time and Events Schedule in Table 4 (see Attachment 9 for additional details)

	,	Study Visits														
Assessments	Screening	Cycle 1						•	le 2ª		Cycl	e 3-6 ^a	Cycle 7-24 ^a	FU	ЕОТ	Safety FU
Visit Number	0	1	2	3	4	5	1	2	3	4	1	2	1	1-6		
	≤21 days before															
Day/Week/Month	Cycle 1 Visit 1	0d	1d	1w	2w	3w	1d	1w	2w	3w	1d	2w	1d	Monthly		
Visit Window		_	_	±1d	±1d	±1d	±4d	±1d	±1d	±1d	±4d	±1d	±4d	±7d	±2d	±7d
Clinical Assessments																
Informed consent	X^{b}															
Eligibility criteria	X															
Demographics	X															
Medical history ^c	X															
Height and body weight	X														X	
Physical examination	X	X													X	
Vital sign measurements ^d	X	X	X	X	X	X	X	X	X	X	X	X	X		X	
Electrocardiogram ^e	X	X	X	X	X	X	X	X	X	X	X	X	X		X	
X-ray or CT scan	X^{f}						Xg				Xg		X ^g		X	
ECOG performance status	X	X					X				X		X		X	
Adverse events	X	X	X	X	X	X	X	X	X	X	X	X	X	X	X	X
Concomitant medications	X	X	X	X	X	X	X	X	X	X	X	X	X	X	X	X
Administration of daratumumab		X														
(predose)																1
Administration of daratumumab			X	X	X	X	X	X	X	X	X	X	X			
Administration of lenalidomide			X (1	Days 1	-21)		2	X (Day	s 1-21)	X (Day	rs 1-21)	X (Days 1-21)			
Administration of dexamethasone		X	X	X	X	X	X	X	X	X	X (4 w	eekly)	X (4 weekly)			
Laboratory Assessmentsh																
Biochemistry ⁱ	X	X	X	X	X	X	X	X	X	X	X	X	X	X	X	
Hematology ^j	X	X	X	X	X	X	X	X	X	X	X	X	X	X	X	
Flow cytometry	X	X	X	X	X	X	X	X	X	X	X	X	X	X	X	
Pregnancy test ^k	X	X					X				X		X	X	X	
Immunogenicity	X						X				X		X	X	X	
Hepatitis B, cytomegalovirus	X															
Complement (CH50) ¹	X						X				X		X		X	
Serum daratumumab level ^m		X	X	X	X	X	X	X	X	X	X	X	X	X	X	
Blood type assessment	X															
Direct & indirect Coombs tests ⁿ	X	X	X	X	X	X	X	X	X	X	X	X	X	X	X	

Table 1: Phase 1 Time and Events Schedule

Note: As of Amendment 8, all subjects are to follow the Time and Events Schedule in Table 4 (see Attachment 9 for additional details)

		Screening Cycle 1 Cycle 2a Cycle 3-6a Cycle 7-24a FU EOT 0 1 2 3 4 5 1 2 3 4 1 2 1 1-6 — 21 days before Cycle 1 Visit 1 0d 1d 1w 2w 3w 1d 2w 1d Monthly — — — — ±1d ±1d ±4d ±1d ±4d ±1d ±4d ±1d ±4d ±2d ±2d X Image: Cycle 7-24a FU EOT EOT EOT —														
Assessments	Screening	Cycle 1						Сус	le 2ª		Cycle 3-6 ^a		Cycle 7-24 ^a	FU	ЕОТ	Safety FU
Visit Number	0	1	2	3	4	5	1	2	3	4	1	2	1	1-6	_	_
Day/Week/Month	≤21 days before Cycle 1 Visit 1	0d	1d	1w	2w	3w	1d	1w	2w	3w	1d	2w	1d	Monthly	_	_
Visit Window		_	_	±1d	±1d	±1d	±4d	±1d	±1d	±1d	±4d	±1d	±4d	±7d	±2d	±7d
Prognostic factors	X															
Soluble CD38	X			X									X			
Response Assessments																
Bone marrow	X^{f}						X^g				X^g				X^g	
IgA, IgM, IgG (M-component serum)	X	X			X		X				X		X	X	X	
M-component (24-hour urine sample) ^o	X	X			X		X				X		X	X	X	
Free light chain kappa, lambda, and ratio (serum)	X	X			X		X				X		X	X	X	
New cancer assessment ^p																X

Key: CT = computed tomography; d = day; ECG = electrocardiogram; ECOG = Eastern Cooperative Oncology Group; EOT = End of Trial; FU = Follow-up; Ig = immunoglobulin; w = week

- All cycles are 28-day cycles; the first visit of a cycle should be 4 weeks after the start of the previous cycle.
- Informed consent may be obtained outside of the Screening Visit window, ie, before the Screening Visit date.
- Signs and symptoms (nonserious adverse events) occurring between the Screening Visit (before the first infusion) and the first study drug treatment at Cycle 1 Visit 1 should be recorded as medical history.
- d Vital signs, defined as blood pressure, pulse, and temperature will be measured at the following time points on days when daratumumab infusions are given: just before the planned infusion start time; at 15-minute intervals during the first 2 hours of the infusion; at 60-minute intervals after the first 2 hours during the infusion; at the end of the infusion; and after the infusion at 10 minutes, 30 minutes, 1 hour, and 2 hours.
- Electrocardiograms (ECGs) will be performed at the Screening Visit (before the first infusion), before and after each daratumumab infusion, and at the EOT Visit. Three baseline ECGs should be performed before the first infusion of study drug. Before the ECGs are recorded, the subjects must be resting in a horizontal position for at least 20 minutes
- The computed tomography scan and bone marrow biopsy/aspirate may have been performed within 6 weeks before Cycle 1 Visit 1.
- To be completed as indicated to confirm response at the subsequent bone marrow biopsy visit or to investigate new symptoms, and at physician discretion.
- h Unless otherwise stated, all blood and urine samples must be taken before administration of daratumumab.
- Blood samples drawn for biochemistry assessments will be analyzed for the following: sodium, potassium, blood urea nitrogen, creatine, aspartate aminotransferase, alanine aminotransferase, alkaline phosphatase, bone-specific alkaline phosphatase, albumin, calcium, glucose, total creatinine kinase, total bilirubin, lactic dehydrogenase, uric acid, β₂-microglobulin, and C-reactive protein.
- Blood samples drawn for hematology assessments will be analyzed for the following: red blood cell count, hemoglobin, hematocrit, mean corpuscular volume, mean corpuscular hemoglobin, mean corpuscular hemoglobin concentration, white blood cell count with differential, platelet count, and reticulocyte count.

Table 1: Phase 1 Time and Events Schedule

Note: As of Amendment 8, all subjects are to follow the Time and Events Schedule in Table 4 (see Attachment 9 for additional details)

- Blood samples for serum pregnancy tests will be collected at the Screening Visit (before the first infusion), every 4 weeks during the treatment and follow-up periods, and at the EOT Visit.
- Blood samples for analysis of complement (CH50) must be drawn 2 hours after the end of infusions.
- m Blood samples will be collected for pharmacokinetic assessments at the following time points: before infusion and at the end of infusion on all daratumumab infusion days; at 2, 5, and 12 hours after the end of infusion at Cycle 1 Visit 2 (first full-dose daratumumab infusion); at 2 hours after the end of infusion at Cycle 2 Visit 4; at each Follow-up Visit; and at the EOT Visit.
- Direct and indirect Coombs tests will be performed at all daratumumab infusion visits (before infusion and 2 hours after the end of infusion) and all follow-up visits until no antibodies are detected. These tests will also be performed at the EOT Visit for all subjects, including those who withdraw from the study.
- o In addition to quantitation of M-component, urinalysis for total protein (including albumin) and creatinine clearance will be performed.
- ^p Subjects will be contacted and asked about the occurrence of new cancers every 6 months for 3 years after their last dose of lenalidomide.

Table 2: Phase 2 Time and Events Schedule

Note: As of Amendment 8, all subjects are to follow the Time and Events Schedule in Table 4 (see Attachment 9 for additional details)

		Study Visits														
Assessments	Screening	Cycle 1						Сус	le 2ª		Cycle 3	8-6 ^a	Cycle 7+	FU ^r	ЕОТ	Safety FU
Visit Number	0	1	2	3	4	5	1	2	3	4	1	2	1		_	
De West Messale	≤21 days before Cycle 1	0d Phase 1	1.1			2	1.1			2	1.1		1.1	0.0		
Day/Week/Month Visit Window	Visit 1	only	1d	1w ±1d	2w	3w ±1d	1d	1w	2w	3w ±1d	1d ±4d	2w ±1d	1d ±4d	Q8w ±7d	±2d	
			_	±10	±10	±10	±4d	±10	±10	±10	±4a	±10	± 40	±/a	±2a	±/a
Clinical Assessments Informed consent	X ^b														-	
Eligibility criteria	X														-	
Demographics	X															
Medical history ^c	X															
Height and body weight	X														X	
Physical examination	X														X	
Vital sign measurements ^d	X		X	X	X	X	X	X	X	X	X	X	X		X	
Electrocardiogram ^e	X		X	2.	21	21	X	7.	7.	7.	X	71	X		X	
X-ray or CT scan	$X^{f,g}$		- 1 1				Xg				Xg		X ^g	X	X	
ECOG performance status	X						X				X		X		X	
Adverse events	X		X	X	X	X	X	X	X	X	X	X	X	X	X	
Concomitant medications	X		X	X	X	X	X	X	X	X	X	X	X	X	X	
Administration of daratumumab ^q			X	X	X	X	X	X	X	X	X	X	X			
Administration of lenalidomide		Σ	(Day	s 1-21	1)		3	(Day	s 1-2	1)	X (Days 1-21)		X (Days 1-21)			
Administration of dexamethasone			X	X	X	X	X	X	X	X	X (4 wee	ekly)	X (4 weekly)			
Laboratory Assessmentsh																
Biochemistry ⁱ	X		X	X	X	X	X	X	X	X	X	X	X	X	X	
Hematology ^j	X		X	X	X	X	X	X	X	X	X	X	X	X	X	
Pregnancy test ^k	X		X				X				X		X	X	X	

Table 2: Phase 2 Time and Events Schedule

Note: As of Amendment 8, all subjects are to follow the Time and Events Schedule in Table 4 (see Attachment 9 for additional details)

		Study Visits														
Assessments	Screening		Cyc	cle 1					ele 2ª	y V 1510	Cycle 3	5-6 ^a	Cycle 7+	FU ^r	ЕОТ	Safety FU
Visit Number	0	1	2	3	4	5	1	2	3	4	1	2	1			
Day/Week/Month	≤21 days before Cycle 1 Visit 1	0d Phase 1 only	1d	1w	2w	3w	1d	1w	2w	3w	1d	2w	1d	Q8w	_	
Visit Window	_	_	_	±1d	±1d	±1d	±4d	±1d	±1d	±1d	±4d	±1d	±4d	±7d	±2d	±7d
Hepatitis B, C, HIV, and cytomegalovirus	X															
Serum daratumumab level ¹			X								Cycles 3 and 6 only		C12 only	Weeks 4 and 8 after last dose		
Immunogenicity ^p			N	lo ad	ditior	1al sa	mple	requ	ired;	take	n from P	K san	nple (see S	Section 9.2	2.4)	
			X											Week 4 and 8 after last dose		
Blood type assessment	X															
Direct & indirect Coombs tests	X															
Flow cytometry			X	X	X	X	X	X	X	X	X		X	X	X	
CDC and other serum- based markers			X	X	X		X								X	
ADCC			X	X			X									
Biomarkers: Whole blood draw (PBMC and plasma for CD38)			X								C3 only				X	
Pharmacogenomics	X															

Table 2: Phase 2 Time and Events Schedule

Note: As of Amendment 8, all subjects are to follow the Time and Events Schedule in Table 4 (see Attachment 9 for additional details)

			Study Visits													
Assessments	Screening		Cy	cle 1				Cyc	le 2ª		Cycle 3	8-6ª	Cycle 7+	FU ^r	ЕОТ	Safety FU
Visit Number	0	1	2	3	4	5	1	2	3	4	1	2	1		_	_
	≤21 days before Cycle 1	0d Phase 1														
Day/Week/Month	Visit 1	only	1d	1w	2w	3w	1d	1w	2w	3w	1d	2w	1d	Q8w	_	
Visit Window	_		_	±1d	±1d	±1d	±4d	±1d	±1d	±1d	±4d	±1d	±4d	±7d	±2d	±7d
Response Assessments			X	X	X	X	X									
Bone marrow aspirate/bone marrow biopsy ^f	X^{g}										X ^g				X ^g	
IgA, IgM, IgG (M- component serum)	X°		Xº		Xº		Xº				Xº		X	Xº	Xº	
M-component (24-hour urine sample) ^m	X		X				X				X		X	X	X	
Free light chain kappa, lambda, and ratio (serum)	X		X		X		X				X		X	X	X	
New cancer assessment ⁿ																X
New antimyeloma treatment ⁿ																X
Survival ⁿ																X

Key: ADCC = antibody-dependent cell-mediated cytotoxicity; CDC = complement-dependent cytotoxicity; CT = computed tomography; d = day; ECG = electrocardiogram; ECOG = Eastern Cooperative Oncology Group; EOT = End of Trial; FU = Follow-up; Ig = immunoglobulin; w = week

- ^a All cycles are 28-day cycles: the first visit of a cycle should be 4 weeks after the start of the previous cycle.
- Informed consent may be obtained outside of the Screening Visit window, ie, before the Screening Visit date.
- Signs and symptoms (nonserious adverse events) occurring between the Screening Visit (before the first infusion) and the first study drug treatment at Cycle 1 Visit 1 should be recorded as medical history.
- d Vital signs are to be measured on days when daratumumab infusions are administered; before the start of the daratumumab infusion and at the end of the infusion.
- ^e Electrocardiograms (ECGs) will be performed at the Screening Visit (before the first infusion), before and after daratumumab infusion on Day 1 of each cycle, and at the EOT Visit. Three baseline ECGs should be performed before the first infusion of study drug. Before the ECGs are recorded, the subjects must be resting in a horizontal position for at least 20 minutes
- The computed tomography scan and bone marrow biopsy/aspirate may have been performed within 6 weeks before Cycle 1 Visit 1.
- To be completed at Screening for clinical staging, at Cycle 3 Day 1, and to confirm sCR, CR, or relapse from CR. May also be performed to investigate new symptoms or at the physician discretion. A portion of the bone marrow aspirate or biopsy will be utilized for biomarker analyses.
- b Unless otherwise stated, all blood and urine samples must be taken before administration of daratumumab. Samples must be sent to the central laboratory.
- Blood samples drawn for biochemistry assessments will be analyzed for the following: sodium, potassium, blood urea nitrogen, creatinine, aspartate aminotransferase, alanine aminotransferase, alkaline phosphatase, bone-specific alkaline phosphatase, albumin, calcium, glucose, total creatine kinase, total bilirubin, lactic dehydrogenase, uric acid, β₂-microglobulin, and C-reactive protein.

Table 2: Phase 2 Time and Events Schedule

Note: As of Amendment 8, all subjects are to follow the Time and Events Schedule in Table 4 (see Attachment 9 for additional details)

- Blood samples drawn for hematology assessments will be analyzed for the following: red blood cell count, hemoglobin, hematocrit, mean corpuscular volume, mean corpuscular hemoglobin, mean corpuscular hemoglobin concentration, white blood cell count with differential, platelet count, and reticulocyte count.
- k Blood samples for serum pregnancy tests will be collected at the Screening Visit (before the first infusion), every 4 weeks during the treatment and follow-up period, and at the EOT Visit.
- If on a daratumumab dosing day, one sample to be collected before (up to 2 hours before but not after the start of infusion) and one sample immediately after (up to 2 hours after but not before the end of infusion) daratumumab administration. For additional information refer to Section 9.2.4.
- In addition to quantitation of M-component, urinalysis for total protein (including albumin) and creatinine clearance will be performed.
- ⁿ Subjects will be contacted and asked about the occurrence of new cancers every 3 months for 3 years after their last dose of lenalidomide. Survival data will also be collected.
- Serum sample will be split into 2 aliquots, with 1 reserved for potential follow-on testing if daratumumab interference with IFE is suspected.
- ^p In addition, any time an infusion-related reaction is observed during the study, an unscheduled blood sample should be drawn as soon as possible after the reaction for potential immune response analysis.
- The daratumumab dose does not need to be recalculated for weight changes that are <10% from baseline.
- For subjects without disease progression.

Table 3: Time and Events Schedule as of Amendment 7 (see also Attachment 8)

	Treatn	ent Phase	End-of-Treatment	Follow-up	
	Start of First Cycle with Amendment 7 ^a	Every Cycle Until Treatment Discontinuation (±4 days)	EOT Visit (3 to 5 weeks after the last dose of study drug)	Every 6 months for 3 years after last dose of study drug ^g (±7 days)	
Study Procedures					
Informed consent	X				
Administration of Daratumumab	X (Day 1)	X (Day 1)			
Administration of Lenalidomide	X (Days 1-21)	X (Days 1-21)			
Administration of Dexamethasone ^b	X (4 weekly)	X (4 weekly)			
Disease assessments ^c	X	X	X		
SAEs ^d	X	X	X		
Pregnancy testing ^e		X (every 4 cycles)	X		
Best response and new antimyeloma therapy ^f			X	X	
New cancer assessment ^f			X	X	
Surviva ^f			X	X	
Immunogenicity and associated serum daratumumab level ^g			Weeks 4 and 8 (±1 week) after last dose of study drug ^h		

EOT=End-of-Trial; SAE=serious adverse event

- This will be the first cycle after the subject completes a cycle and all scheduled assessments under protocol Amendment INT-6 (there should not be a restarting of the cycle number). All cycles are 28-day cycles: the first visit of a cycle should be 4 weeks after the start of the previous cycle.
- The administration of dexamethasone may be adjusted at the discretion of the investigator, however, dexamethasone should always be administered at a dose of 20 mg IV on daratumumab infusion days.
- ^c Disease assessments/response evaluations are to be performed per local institutional practice.
- Includes secondary malignancies. Concomitant medication information associated with SAEs will also be collected (See Attachment 8 for more details).
- e Samples will be analyzed by a local laboratory.
- Subjects will be contacted and asked about the occurrence of new cancers, best response, new antimyeloma treatment, and information on survival every 6 months for 3 years after the last dose of study drug or until termination of the study by the sponsor, whichever occurs first.
- Subjects will have blood samples taken only for immunogenicity, the associated daratumumab concentration will be determined from the same sample. In addition, any time an infusion-related reaction is observed during the study, an unscheduled blood sample should be drawn as soon as possible after the reaction for potential immune response analysis.
- The Week 4 sample will be collected at the EOT visit.

Table 4: Time and Events Schedule as of Amendment 8 (see also Attachment 9)

Study Procedure	Start of First Dosing with Amendment 8 ^a
Informed Consent Amendment 8	X
Administration of Daratumumab	X (Day 1)
Administration of Lenalidomide	X (Day 1-21)
Administration of Dexamethasone ^b	X (4 weekly)
Disease assessments ^c	X
SAEs	X
Secondary Primary Malignancy ^d	X
Immunogenicity Sample ^e	1x before start of the last dose under study Amendment 7

- a. This will be the first dosing once Amendment 8 is fully approved at the site, and after the subject completes a final cycle and all scheduled assessments under protocol Amendment 7.
- b. The administration of dexamethasone may be adjusted at the discretion of the investigator; however, dexamethasone should always be administered at a dose of 20 mg intravenously on daratumumab infusion days. See Section 6.3 for further detail.
- c. Disease assessments/response evaluations are to be performed per local institutional practice.
- d. Subjects will be contacted regarding the occurrence of new SPMs every 3 months by phone (month 3, month 9, etc..) or in a site visit (month 6, month 12, etc...). In cases where subjects become aware of the occurrence of a new SPM, they will instructed to report it as soon as possible to their study investigator.
- e. As of Amendment 8, blood sample collection will stop and will not be performed after the last dose of daratumumab. One final sample should be collected before the last infusion of daratumumab per Amendment 7 and sent to the central laboratory. Sample will also be assessed for serum daratumumab concentration to ensure proper interpretation of immunogenicity data.

ABBREVIATIONS

Abbreviation Definition

ADCC antibody-dependent cell-mediated cytotoxicity

AE adverse event

ALT alanine aminotransferase

anti-HBc antibodies to hepatitis B core antigen anti-HBs antibodies to hepatitis B surface antigen

AST aspartate aminotransferase

AUC area under the concentration-time curve auto-SCT autologous stem cell transplantation CDC complement-dependent cytotoxicity

CL total systemic clearance of drug after IV administration

C_{max} maximum concentration in serum

C_{min} minimum or trough concentration in serum

CR complete response CrCl creatinine clearance

CRO contract research organization

CSR Clinical Study Report CT computed tomography

CTCAE Common Terminology Criteria for Adverse Events, version 4.0

DCF Data Clarification Form
DLT dose-limiting toxicity
DNA deoxyribonucleic acid
DVT deep vein thrombosis
ECG electrocardiogram

ECOG Eastern Cooperative Oncology Group

eCRF electronic case report form

EOT End of Trial EU European Union

FDA Food and Drug Administration FEV1 forced expiratory volume in 1 second

GCP Good Clinical Practice

G-CSF granulocyte-colony stimulating factor

HBsAg hepatitis B surface antigen
HIV human immunodeficiency virus
IAT indirect antiglobulin test
ICF Informed consent form

ICH International Conference on Harmonisation IDMC Independent Data Monitoring Committee

IEC Independent Ethics Committee

Ig immunoglobulin IL interleukin

IMiD immunomodulatory drugs IRB Institutional Review Board

ITT Intent-to-Treat IV intravenous

Len/Dex lenalidomide and dexamethasone

mAb monoclonal antibody
MR minimal response
MTD maximum tolerated dose

NaCl sodium chloride
NK natural killer
ORR overall response rate
PD progressive disease
PE pulmonary embolism
PFS progression-free survival

JNJ-54767414 daratumumab

PK pharmacokinetic(s)

PO orally PP Per-Protocol

PQC product quality complaint

PR partial response RBC red blood cell

RhD Rh blood group, D antigen RP2D recommended Phase 2 dose SAE serious adverse event SPM second primary malignancy

 $t_{1/2}$ elimination half-life

 T_{max} time to maximum concentration in serum

ULN upper limit of normal

US United States

 $\begin{array}{ll} V & \text{volume of distribution} \\ V_{\text{cen}} & \text{central volume of distribution} \\ VGPR & \text{very good partial response} \end{array}$

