9. STUDY EVALUATIONS

9.1. Study Procedures by Visit

9.1.1. Overview

The following sections give a brief overview of the Screening Period, Treatment Period, Follow-up Period, and EOT Visit. The Time and Events Schedule summarizes the frequency and timing of safety, efficacy, pharmacokinetic, pharmacodynamic, and other measurements applicable to this study. As of Amendment 8, follow the schedule of events outlined in Table 4 and additional details are provided in Attachment 9.

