9.2.2. Clinical Laboratory Assessments

Unless otherwise stated, all blood and urine samples must be taken before administration of daratumumab. Blood tests, such as a blood type assessment, performed after the infusion of daratumumab may be confounded by the drug. The scheduling for all assessments listed in this

72

section is detailed in Table 1 and Table 2. As of Amendment 7, clinical laboratory assessments (safety and efficacy) will be performed locally and based on local institutional practice. Pregnancy testing will continue, every 4 weeks during treatment and at the EOT visit, but will be performed by a local laboratory (See Table 3 and Attachment 8).

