9.2.2.4. Pregnancy Test

As of Amendment 8, serum pregnancy tests will continue to be performed by the local laboratory on samples collected every 4 weeks during the Treatment Period (see Table 3).

A blood sample will be drawn at the Screening Visit or before the first infusion from all women of childbearing potential. The sample will be shipped to the central laboratory (BARC) for immediate analysis of human chorionic gonadotropin. Pregnant women will not be allowed to take part in this study and will be considered as screening failures.

Women are considered of childbearing potential unless they have undergone hysterectomy or tubal ligation within 1 year or have been postmenopausal for at least 1 year before the Screening Visit or before the first infusion

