As of Amendment 7, subjects who are in Follow-up (Table 2) will complete an EOT visit and immunogenicity assessments (if not yet completed) and will enter the modified Follow-up in the Time and Events Schedule (Table 3). Follow-up with Amendment 7 will include collection of best response and new antimyeloma therapy (disease assessments should be per local institutional practice), survival information, and occurrence of new cancers every 6 months for 3 years after the last dose of study drug or termination of the study by the sponsor, whichever occurs first.

Efficacy Evaluations

Investigators should monitor and assess the subjects for response to treatment or disease progression according to local institutional practice.

Safety Evaluations

Study drug administration and SAEs (including secondary malignancies) will be collected. Pregnancy testing will continue every 4 weeks during the Treatment Period and at the EOT visit. Concomitant medications associated with SAEs will also be collected. Serious adverse event reporting should continue as described in Section 12.6.2. The SAEs should be entered in the subject file/source notes.

Source Documentation

At a minimum, the type and level of detail of source data available for a study subject should be consistent with that commonly recorded at the site as a basis for standard medical care. This should also include: subject identification and study identification; study discussion and date of updated informed consent; dates of visits; drug dispensing/return records and study drug administration information.

117

Attachment 9: Limited Schedule of Events for Subjects Continuing Daratumumab as of Amendment 8

Protocol Amendment 8 will allow those subjects who are receiving daratumumab after the final analysis to continue receiving study drug. All subjects have received at least 24 months of therapy with daratumumab, or have discontinued.

Dosage and Administration

Daratumumab, lenalidomide, and dexamethasone will be administered according to the regimen established prior to Amendment 8.

Visits will occur on a monthly schedule, assessments done need to be captured in the source notes only.

Daratumumab will be provided by the sponsor until daratumumab in combination with lenalidomide and dexamethasone has been approved for use in patients with relapsed/ refractory multiple myeloma and is commercially available in the respective countries.

Treatment Period

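### Table 3 schedules pregnancy tests every 4 cycles (112 days) where the rest of the protocol requires every 4 weeks, and Table 4, now in force, has no pregnancy-test row

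*Protocol*

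**What the plan says.** Table 3, the Amendment 7 schedule, gives the pregnancy-test frequency during treatment as "X (every 4 cycles". A footnote to the same table states "All cycles are 28-day cycles".

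Five other places in the current protocol give a different interval:

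- Table 1, pregnancy-test footnote: "every 4 weeks during the treatment and follow-up periods, and at the EOT Visit".
- Table 2, footnote k: "every 4 weeks during the treatment and follow-up period, and at the EOT Visit".
- Section 9.2.2, describing the position as of Amendment 7 and citing Table 3 and Attachment 8: "Pregnancy testing will continue, every 4 weeks during treatment and at the EOT visit".
- Section 9.2.2.4, describing the position as of Amendment 8: "samples collected every 4 weeks during the Treatment Period (see Table 3".
- Attachment 8, Safety Evaluations, the companion text to Table 3: "Pregnancy testing will continue every 4 weeks during the Treatment Period and at the EOT visit".

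Section 9.1.1 then makes Table 4 the governing schedule: "As of Amendment 8, follow the schedule of events outlined in Table 4". Table 4 lists consent, the three study drugs, disease assessments, SAEs, second primary malignancies and an immunogenicity sample. Lenalidomide continues on Days 1 to 21. There is no row for a pregnancy test.

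**The concern.** There are two linked faults. The first is that the Table 3 cell cannot be reconciled with the text that cites it. Sections 9.2.2 and 9.2.2.4 both refer the reader to Table 3, so someone checking the schedule arrives at the one entry that disagrees.

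The second is that the table now in force is silent on a test that Section 9.2.2.4 says continues. A site working from Table 4 alone would find no pregnancy test. A site that follows the Section 9.2.2.4 reference would find a 16-week interval.

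What is at stake is the safety of women of childbearing potential who are still on treatment. Section 12.6.3 describes lenalidomide as related to thalidomide and warns of birth defects and fetal death. Sections 10.1 and 10.2 require treatment to stop on pregnancy, so the testing interval bears on how soon exposure ends. The items that Section 17.8 names for monitoring visits do not include pregnancy tests, so a missed test might not be noticed there.

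**Working it through.** **Inputs.** Cycle length is 28 days (Table 3 footnote). The Table 3 frequency is one test per 4 cycles. The frequency in the other five places is one test per 4 weeks. Amendment 7 was issued on 06 October 2015 and Amendment 8 on 29 September 2016 (list of protocol amendments).

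**Interval.**

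- Table 3 cell: 4 cycles x 28 days = 112 days; divided by 7 days a week, this is 16 weeks.
- Other text: 4 weeks x 7 days = 28 days, which is one cycle.
- Ratio: 112 days divided by 28 days = 4.

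**Tests per year.** A year is taken as 365.25 days.

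- Table 3 cell: one year divided by 112 days = 3.26 tests.
- Other text: one year divided by 28 days = 13.04 tests.

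**Over the life of Table 3.** From 06 October 2015 to 29 September 2016 is 359 days. Divided by the cell's 112 days, this is 3.21, so 3 completed intervals. Divided by the text's 28 days, it is 12.82, so 12 completed intervals. Issue dates stand in here for the period when Table 3 was in use, because site approval dates are not given. The fourfold ratio does not depend on this.

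**Which interval is intended.** Five statements agree on 4 weeks and one cell differs. The cell's own column covers every cycle until treatment stops, and one test per cycle is exactly one test per 4 weeks. The likeliest explanation is that cycles was typed for weeks.

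**Whether the Table 4 gap is a decision to stop.** Section 9.2.2.4 opens its pregnancy-test requirement with Amendment 8 and says that serum tests continue at the local laboratory. That rules out reading the missing row as an end to testing. The gap does not look like a loss in the text copy either: footnotes a to e of Table 4 are all present and attached to entries, and none concerns pregnancy.

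**The case against.** The strongest reply is that Table 3 has been superseded. As of Amendment 8 all subjects follow Table 4, and two of the five agreeing statements are footnotes to tables that carry the same redirection. Only Sections 9.2.2 and 9.2.2.4 and Attachment 8 speak to the period from Amendment 7 on, and only Section 9.2.2.4 speaks for Amendment 8. In that section the 4-week interval and the reference to Table 3 are in the same sentence, so a reader has just seen the right number. This stands as a reason to think few sites would be misled. It does not make the cell right, and the reference in Section 9.2.2.4 keeps Table 3 in use after Amendment 8.

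A second reply is that the missing Table 4 row may be deliberate. The Amendment 7 note in the synopsis includes pregnancy testing in the limited safety information, while the Amendment 8 note limits that information to SAEs and second primary malignancies. That limit concerns what the study collects. Section 9.2.2.4 still requires the test to be done, and a schedule of events should show it.

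A third reply is that Attachment 9, the companion to Table 4, may state the testing rule. The copy reviewed stops at its Treatment Period heading, so this cannot be excluded. If it does, the omission matters less, but the Table 3 cell, the absent row and the misdirected reference all remain.

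Other safeguards also apply: the US and EU lenalidomide programmes (Section 9.1.3), the label warnings throughout the study (Section 12.6.3) and the contraception requirement (Exclusion Criterion 27). These reduce the risk and limit how serious the point is. Finally, the count of 3 against 12 intervals describes a past period that no correction can change. It shows scale only.

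**Conclusion.** The concern holds. The Table 3 cell is wrong as written: it gives 112 days between tests where the protocol otherwise requires 28, a fourfold difference. Table 4 omits a test that Section 9.2.2.4 requires, and Section 9.2.2.4 refers to the wrong table. The conclusion rests on the 28-day cycle in Table 3's footnote and on current protocol text alone; it assumes nothing about Attachment 9.

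This is a safety-schedule error that should be corrected. It affects only women of childbearing potential still receiving treatment, a number the documents do not give. It has no bearing on the endpoints, the sample size or any analysis.

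**What to change.** Make three edits:

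1. In Table 3, change the treatment-phase pregnancy-test cell to every cycle (every 4 weeks).
2. In Table 4, add a row for a serum pregnancy test every 4 weeks during treatment, for women of childbearing potential, at the local laboratory.
3. In Section 9.2.2.4, change the cross-reference from Table 3 to Table 4.

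The cost is one cell, one row and one reference. No procedure is added, because Section 9.2.2.4 already requires 4-weekly local testing and Attachment 9 already schedules monthly visits. When making the edits, the sponsor should check that the full Attachment 9 gives the same interval.
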